6.4. Adenoviral Vectors for Gene Therapy

6.4.1. Adenoviral Safety

Adenoviral vectors have been used extensively to deliver a variety of gene products to human subjects, including cancer subjects. Although adenoviral vectors are immunogenic, virtually all recipients have pre-existing humoral immunity to adenoviruses and they are generally considered a safe and well tolerated vehicle for gene delivery. Numerous studies have utilized adenoviral vectors to achieve intratumoral expression of a variety of genes. In a Phase I/II clinical trial of subjects with prostate cancer, direct intraprostatic injection of a replication-defective adenoviral vector encoding bacterial nitroreductase (dose levels 5×10^{10} - 1×10^{12} viral particles [vp]) was well tolerated, with minimal adverse events (AEs) (Patel et al. 2009). A Phase I study of subjects with oral leukoplakia implemented multiple intraepithelial injections of recombinant adenovirus (rAd)-p53 (1×10^8 vp/cm²) and demonstrated good tolerance of the vector, with no evidence of dose-limiting toxicity (DLTs) (Zhang et al. 2009). In another Phase I/II study of subjects with chemoradiation-resistant advanced esophageal carcinoma, intratumoral injections of adenovirus vector containing p53 (Ad.5CMV-p53) were well tolerated at doses ranging from 10×10^{11} to 25×10^{11} vp, with no DLTs, and generally mild to moderate adverse events (AEs) (Shimada et al. 2006). The most common AEs were fever (all 10 subjects), pain (30% of subjects), and hyperglycemia, which was attributed to the use of total parental nutrition (30% of subjects). Hypocalcemia was reported in two subjects (20%) and one subject each (10%) experienced activated partial thromboplastin time (aPTT) prolongation, abnormally high serum amylase, and abnormally high serum creatinine.

In a Phase I study of subjects with advanced pancreatic, colorectal, or primary liver tumors, intratumoral injection of an adenoviral vector encoding hIL-12 (Ad.hIL-12) was well tolerated at doses of up to 3×10^{12} vp. Common AEs were similar to symptoms observed with gene delivery by other adenoviral vectors, including transient, mild to moderate fever, malaise, sweating, and lymphopenia (Sangro et al. 2004).

A recent randomized, open-label, Phase III study compared a regimen of surgical resection, adenovirus-mediated gene therapy (intraoperative perilesional sitimagene ceradenovec), intravenous ganciclovir, and standard of care interventions versus surgical resection plus standard of care interventions in 250 subjects with newly diagnosed high-grade glioma amenable to resection. Results showed that although the time to death or re-intervention was prolonged, OS was not improved for the investigational regimen relative to the standard of care regimen (Westphal et al. 2013). This apparent difference may have been due to the composite primary endpoint and/or that while OS is a robust endpoint, there is no discussion of effect size and for recently-diagnosed tumors it might be less suitable to capture meaningful treatment effects for the initial stages of disease because of uncontrolled therapy at relapse (*ibid*). Nevertheless, the authors concluded that the treatment had an increased hazard ratio for the primary analysis with a positive overall benefit-risk ratio, with similar AEs (hemiparesis [often transient], hyponatremia, and seizures, but no cerebral hemorrhages nor hematomas), as compared with the standard-of-care regimen.

6.4.1.1. Safety of Intratumoral Injection of IL-12 Gene Vectors

In contrast with the systemic toxicity resulting from administration of recombinant IL-12 protein, local administration of IL-12 via injection of plasmid or adenoviral vectors containing the hIL-12 gene has proven to be well tolerated in subjects with various cancers, and therefore appears to provide an effective delivery method for this potent immunomodulatory cytokine. Several studies have investigated the safety of intratumoral expression of IL-12 in subjects with metastatic melanoma. A Phase I study investigated intratumoral expression of IL-12 together with the co-stimulatory molecule B7.1 via two separate canarypox virus viral vectors (ALVAC) in subjects with metastatic melanoma and reported mild to moderate injection site reactions, fever, chills, myalgia, and fatigue as AEs (Triozzi et al. 2005). However, all subjects also developed antibodies to ALVAC. Notably, serum IL-12 and IFN- γ levels were not increased after treatment. Another Phase I trial showed that delivery by electroporation of a plasmid containing IL-12 to tumors in subjects with metastatic melanoma resulted in minimal systemic toxicity, with transient pain after electroporation being the most common AE (Daud et al. 2008). Results from another Phase I study showed that intratumoral injection of DNA encoding hIL-12 in subjects with metastatic melanoma was well tolerated overall (Heinzerling et al. 2005). Eight of nine subjects experienced a transient response at the intratumoral injection site, and some subjects who had tumor responses also showed some increases in systemic in IL-12, interferon gamma-induced protein 10 (IP-10), and IFN- γ .

Localized production of IL-12 also has been reported as well tolerated in subjects with other malignancies. For example, a Phase I study in 17 subjects with metastatic pancreatic, colorectal, or primary liver cancer examined intratumoral injection of dendritic cells engineered to secrete IL-12 via a rAD vector (Mazzolini et al. 2005). In that study, the most common AEs were lymphopenia, fever, and malaise. Subjects also developed antibodies to the adenoviral capsid proteins. Intraperitoneal injection of a plasmid containing the hIL-12 gene in women with chemotherapy-resistant, recurrent, ovarian cancer also was found to be generally safe and well tolerated (Anwer et al. 2010). Low-grade fever and abdominal pain were the most common AEs. Plasmid DNA was not detected in the subjects' serum samples, and treatment-related increases in IFN- γ levels were observed in pleural fluid, but not in serum. Similar data were reported in a study of subjects with advanced pancreatic, colorectal, or primary liver malignancies who received intratumoral injections of adenoviral vectors encoding hIL-12 at doses ranging from 2.5×10^{10} to 3×10^{12} vp (Sangro et al. 2004). In that study, treatment was well tolerated and a maximum tolerated dose (MTD) was not reached. Transient lymphopenia was observed in 86% of subjects, and the severity was increased at higher vector doses. Transient, mild to moderate fever, sometimes accompanied by malaise and sweating, was observed in ~ 60% of subjects during the first 2 days after the injection. Five of the 21 subjects (24%) experienced nausea and/or vomiting on the day of the injection. No cumulative toxicity was observed. These events were deemed related to injection of the virus and not to transgene expression.

This image is a high-contrast, black-and-white scan of a document page. The content is heavily pixelated and obscured. A large, dark rectangular area occupies the upper portion of the page. Within this area, there are several white horizontal bars of varying lengths. A few small black rectangles are also visible. The overall quality is very poor, suggesting a low-resolution scan or a heavily processed image.

[REDACTED]

[REDACTED]

[REDACTED]

[REDACTED]

6.5.3. Veledimex

Veledimex is a diacylhydrazine that is fully active at the RTS receptor. Drug product is formulated as a semi-solid containing veledimex as a dry powder and excipients. This formulation has been encapsulated in gelatin capsules for oral administration in clinical trials.

[REDACTED]

6.5.4. Cemiplimab-rwlc

Cemiplimab-rwlc (Libtayo ®), is a high affinity hinge-stabilized IgG4P human antibody to the PD-1 receptor (PDCD1, CD279) that blocks PD-1/PD L1-mediated T cell inhibition. Cemiplimab-rwlc was isolated from Regeneron's VelocImmune™ human antibody mouse platform and contains a human light chain variable domain fused to human kappa constant domain and a heavy chain variable region in a human IgG4 Fc format. The IgG4 Fc domain contains a serine to proline mutation in the hinge region to promote dimer stabilization, designated IgG4P.

[REDACTED]

This image consists of a high-contrast, black-and-white graphic. It features a large, solid black rectangular area in the center. Above this central black area, there are several thin, horizontal white lines of varying lengths. Below the central black area, there are several thin, horizontal black lines of varying lengths. The entire composition is set against a white background and is enclosed within a thick black border.

both species is 1:40 resulting in a human equivalent dose (HED) of 2.4×10^{12} vp or 2.4×10^{11} vp

The image consists of a series of horizontal bars, primarily black, set against a white background. There are several white horizontal spaces of varying widths scattered among the black bars. The image has a high-contrast, binary black-and-white appearance. It is heavily pixelated, suggesting it is a scan of a document or a specific type of data visualization. The overall pattern is a series of horizontal segments, with the black segments being the dominant feature.

6.9. Summary of Safety

Please see the Investigator's Brochure for the most current safety information.

[REDACTED]

[REDACTED]

[REDACTED]

[REDACTED]

7. STUDY OBJECTIVES

7.1. Primary Objective

To determine the safety and efficacy of intratumoral Adenovirus RheoSwitch Therapeutic System® (RTS) human interleukin 12 (Ad-RTS-hIL-12) and oral (PO) veledimex (RTS activator ligand) in combination with cemiplimab-rwlc (Libtayo®) when treating subjects with recurrent or progressive glioblastoma. This determination will be based on the safety profile observed for drug safety and on an estimate of Overall Survival (OS) for efficacy, respectively.

7.2. Secondary Objectives

- To determine the survival rates at 6, 12, 18 and 24 months
- To determine the progression free survival (PFS), and rate of pseudo-progression (PSP) at 6, 12, 18 and 24 months
- To determine the Investigator's assessment of response, including tumor objective response rate (ORR) at 6, 12, 18 and 24 months
- To determine the tumor response rates at 6, 12, 18 and 24 months

8. STUDY DESIGN

8.1. Overall Study Design

This is a multicenter Phase II study of an intratumoral injection of Ad-RTS-hIL-12 [REDACTED] and veledimex (20 mg) administered PO in combination with cemiplimab-rwlc (350 mg) administered intravenously (IV) in subjects with recurrent or progressive glioblastoma. This study will determine the safety and efficacy of Ad-RTS-hIL-12 + veledimex when administered in combination with cemiplimab-rwlc, based on the safety profile observed and overall survival, respectively.

This study includes a Screening Period, Treatment Period, and Survival Follow-up. After the informed consent form (ICF) is signed, subjects will enter the Screening Period to be assessed for eligibility. Subjects will receive cemiplimab-rwlc on Day -7 (± 3 days). On Day 0 (day of Ad-RTS-hIL-12 administration) subjects will take one dose of veledimex 3 ± 2 hours prior to injection and Ad-RTS-hIL-12 [REDACTED] will be administered by freehand injection. Ad-RTS-hIL-12 will be delivered intratumorally or at the margin of the tumor for a total volume of 0.1 mL following resection (subtotal or gross total). The total amount delivered to each site will be recorded in the eCRF. If the total administered volume is less than planned, the reason will be provided. Care should be taken to avoid intraventricular or basal cisternal injection or other critical locations.

After the Ad-RTS-hIL-12 injection, veledimex will be administered orally for 14 days. The first post craniotomy veledimex dose is to be given on Day 1. Subsequent veledimex doses are to be taken once daily, in the morning. Dosing on Days 2-14 should be at approximately the same time of day (+/- 1 hours) as the Day 1 dosing.

Subjects will receive a dose of cemiplimab-rwlc (350 mg) IV on Day 15 and every three weeks thereafter (Q3W) until documented progression by immunotherapy Response Assessment for Neuro Oncology (iRANO) criteria, unacceptable toxicity, subject withdrawal or completing the follow-up period. Delays in cemiplimab-rwlc dosing due to toxicities are allowed at the discretion of the Principal Investigator in consultation with the Medical Monitor, for up to 14 days.

A formal Safety Review Committee (SRC) will be comprised of the study Investigators and the Medical Monitor.

After the first six patients have been enrolled and administered Ad-RTS-hIL-12 and veledimex in combination with at least one post Ad-RTS-hIL-12 dose of cemiplimab-rwlc, enrollment will be paused to allow for additional safety follow-up and assessment. The SRC will review safety data after the 6th subject has reached Day 28 and decide if enrollment should occur at the same dose and schedule of the investigational products.

8.2. Study Oversight for Safety Evaluation

Safety oversight will occur through the site investigator and medical monitor. A formal SRC, guided by the SRC charter, will include the study investigators, the medical monitor and other appropriate sponsor representatives and will provide overall safety oversight. Additional external medical and scientific experts may also be invited to participate in the reviews as needed and appropriate and as decided by the SRC. If a significant safety event occurs, the SRC will convene to evaluate the safety event(s) and make a recommendation and decision on the enrollment and continued treatment of subjects.

9. SUBJECT SELECTION

Subjects with supratentorial glioblastoma who have not previously been treated with inhibitors of immuno-checkpoint pathways (e.g., anti-PD-1, anti-PD-L1, anti-PD-L2, anti-CD137, or anti-CTLA-4 antibody) or other agents specifically targeting T cells.

9.1. Inclusion Criteria

1. Male or female subject ≥ 18 and ≤ 75 years of age
2. Provision of written informed consent for tumor resection (subtotal allowed), tumor biopsy, samples collection, and treatment with investigational products prior to undergoing any study-specific procedures
3. Histologically confirmed glioblastoma from archival tissue
4. Evidence of tumor recurrence/progression by magnetic resonance imaging (MRI) according to Response Assessment in Neuro-Oncology (RANO) criteria after standard initial therapy. Multifocal disease is allowed.
5. Previous standard-of-care antitumor treatment including surgery and/or biopsy and chemoradiation. At the time of registration, subjects must have recovered from the toxic effects of previous treatments as determined by the treating physician. The washout periods from prior therapies are intended as follows: (windows other than what is listed below should be allowed only after consultation with the Medical Monitor)
 - a. Nitrosoureas: 6 weeks
 - b. Other cytotoxic agents: 4 weeks
 - c. Antiangiogenic agents: 4 weeks
 - d. Targeted agents, including small molecule tyrosine kinase inhibitors: 2 weeks
 - e. Vaccine-based or CAR-T therapy: 3 months
6. Able to undergo standard MRI scans with contrast agent before enrollment and after treatment
7. Karnofsky Performance Status ≥ 70
8. Adequate bone marrow reserves and liver and kidney function, as assessed by the following laboratory requirements:
 - a. Hemoglobin ≥ 9 g/L
 - b. Lymphocytes $>500/\text{mm}^3$
 - c. Absolute neutrophil count $\geq 1500/\text{mm}^3$
 - d. Platelets $\geq 100,000/\text{mm}^3$
 - e. Serum creatinine $\leq 1.5 \times$ upper limit of normal (ULN)
 - f. Aspartate transaminase (AST) and alanine transaminase (ALT) $\leq 2.5 \times$ ULN.
 - g. Total bilirubin $<1.5 \times$ ULN
 - h. International normalized ratio (INR) and activated partial thromboplastin time (aPTT) or partial thromboplastin time (PTT) within normal institutional limits

9. Female of child bearing potential* and sexually active male subjects must agree to practice highly effective contraception prior to the start of the first treatment, during the study, and for at least 4 months after the last dose. Highly effective contraceptive measures include stable use of combined (estrogen and progestogen containing) hormonal contraception (oral, intravaginal, transdermal) or progestogen-only hormonal contraception (oral, injectable, implantable) associated with inhibition of ovulation initiated 2 or more menstrual cycles prior to screening; intrauterine device (IUD); intrauterine hormone-releasing system (IUS); bilateral tubal ligation; vasectomized partner; and or sexual abstinence**.

* Postmenopausal women must be amenorrheic for at least 12 months in order not to be considered of childbearing potential. Pregnancy testing and contraception are not required for women with documented hysterectomy or tubal ligation.

** Sexual abstinence is considered a highly effective method only if defined as refraining from heterosexual intercourse during the entire period of risk associated with the study treatments. The reliability of sexual abstinence needs to be evaluated in relation to the duration of the clinical trial and the preferred and usual lifestyle of the patient.

10. Normal cardiac and pulmonary function as evidenced by a normal ECG with QTc \leq 450 msec and peripheral oxygen saturation (SpO₂) \geq 92% on Room air by pulse oximetry

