12.3.1.7. Clinical Laboratory Assessments

The hematology panel comprises a complete blood count (CBC), including white blood cell (WBC) count with differential, red blood cell (RBC) count, hematocrit, hemoglobin, red blood cell indices, mean corpuscular volume (MCV), and platelet count.

The serum chemistry panel comprises the following parameters: AST, ALT, lactate dehydrogenase (LDH), alkaline phosphatase (ALP), creatinine, total bilirubin, total protein, albumin, amylase, blood urea nitrogen (BUN), glucose, sodium, potassium, chloride, calcium, phosphorus, and bicarbonate.

The coagulation panel includes activated partial thromboplastin time (aPTT) or partial prothrombin time (PTT) and prothrombin time (PT) or INR. The acute phase reactants include erythrocyte sedimentation rate (ESR) and CRP.

The urinalysis panel (dipstick) includes appearance, pH, specific gravity, glucose, protein/albumin, presence of blood, ketones, bilirubin, nitrates, and leukocyte esterase. In addition, a microscopic exam for casts, crystals, and cells may be done if clinically indicated.

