12.3.2.3. Treatment Period: Day 0 (Ad-RTS-hIL-12 injection)

- Physical examination (including neurological examination)
- Karnofsky Performance Status
- Vital signs including SpO₂
- Adverse events evaluation
- Concomitant medications
- Urine or serum pregnancy test
- Hematology Panel (All labs should be collected prior to the subject's pre-op dose of veledimex)
- Coagulation Panel
- Serum Chemistry Panel
- Urinalysis Panel
- ECG
- Dose of veledimex 3 (\pm 2) hours prior to resection, on an empty stomach (excluding other medications) AND compliance diary. Intratumoral Ad-RTS-hIL-12 will be administered by freehand injection.
- [REDACTED]

12.3.2.4. Treatment Period: Day 1

- Once daily veledimex AND compliance diary
- Physical examination (including targeted neurological evaluation)
- Vital signs
- Adverse events evaluation
- Concomitant medications
- Hematology Panel
- Coagulation Panel
- Serum Chemistry Panel
- [REDACTED]
- MRI scan: to be done within 24 hours (a +48hr window is allowed) of Ad-RTS-hIL-12 administration and to be used as the baseline MRI for tumor response assessment
- [REDACTED]

12.3.2.5. Treatment Period: Day 2

- Once daily veledimex AND compliance diary
- Physical examination (including targeted neurological evaluation)
- Vital signs
- Adverse events evaluation
- Concomitant medications
- Hematology Panel
- Serum Chemistry Panel

12.3.2.6. Treatment Period: Day 3

- Once daily veledimex dose AND compliance diary (The Day 3 dose should be held until Day 3 labs have been reviewed. Subjects should not be dosed unless lymphocyte counts, platelet counts, and liver function tests have changed by $\leq 20\%$ from baseline values and the Grade of any abnormality has not increased. Medical monitor consultation is then advised.)
- Physical Examination (including targeted neurological evaluation)
- Vital signs including SpO₂
- Adverse events evaluation
- Concomitant medications
- Hematology Panel
- Coagulation Panel
- Serum Chemistry Panel
- Urinalysis Panel
- ECG

12.3.2.7. Treatment Period: Days 4 through 6

- Once daily veledimex dose AND compliance diary
- Adverse events evaluation
- Concomitant medications

12.3.2.8. Treatment Period: Day 7

- Once daily veledimex dose AND compliance diary
- Physical examination (including targeted neurological evaluation)
- Vital signs including SpO₂
- Weight
- Adverse events evaluation
- Concomitant medications
- Hematology Panel
- Serum Chemistry Panel
- Coagulation Panel
- Urinalysis Panel
- ECG

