9.2. Clinical Laboratory Evaluations

Laboratory assessments will be performed by a central laboratory. All summaries will be based on the units provided by the central laboratory, no conversion will be done.

Summary tables will be presented for clinical laboratory tests with numeric values for subjects in the FAS. Observed results at each visit will be presented.

All relevant clinical laboratory tests will be classified as Low, Normal, and High, or Normal/Abnormal according to the normal ranges. This categorical data will be summarized in shift tables comparing the results at each scheduled post-baseline visit with those at the baseline visit. Extreme post-baseline results will also be summarized.

When there are multiple values within a visit for a particular laboratory variable, the worst value will be taken (worst being the smallest value for criteria below a certain threshold or the largest value for criteria above a certain threshold). If a subject has a value below the threshold and above the threshold, the value furthest from the threshold will be chosen.

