Listing 16.2.7.5	TEAEs leading to Study Discontinuation	Full Analysis Population	L Ae	
Listing 16.2.7.6	TEAEs with CTCAE Toxicity Grade ≥ 3	Full Analysis Population		
Listing 16.2.7.8	Deaths	Overall Safety Population	L Deat	
Listing 16.2.6.6	Survival	Full Analysis Population	L Surv	
Listing 16.2.6.7	Progression Free Survival Data	Full Analysis Population	L Pfs	
Listing 16.2.6.8	Kaplan Meier Survival and Censoring Times	Full Analysis Population	L Surv2	

Listing 16.2.8.5	SI Units and Conversion Factors	Full Analysis Population	L Conv	
Listing 16.2.8.1	Serum Chemistry Data	Full Analysis Population	L Labs	
Listing 16.2.8.2	Hematology and Coagulation Data	Full Analysis Population	L Labs	
Listing 16.2.8.3	Hematology and Coagulation Data	Full Analysis Population	L Labs	
Listing 16.2.8.4	Urinalysis Data	Full Analysis Population	L Labs	
Listing 16.2.9	Pregnancy Test	Full Analysis Population	L Preg	
Listing 16.2.10	Vital Signs	Full Analysis Population	L Vit	
Listing 16.2.11	ECG Data	Full Analysis Population	L Ecg	
Listing 16.2.12	Physical Examination	Full Analysis Population	L Phys	
Listing 16.2.13	Neurological Examination	Full Analysis Population	L Neuro	
Listing 16.2.14	Karnofsky Performance Status	Full Analysis Population	L Kps	
Listing 16.2.15	Visits	Full Analysis Population	L Vis	

Table/Figure Number	Table Title	Population	Tab Name		RAW	SDTM	ADaM	Table
Table 14.1.1	Subject Disposition	All Subjects	Disp			DS	ADSL	Disp table is done
Table 14.1.2	Protocol Deviations	Full Analysis Population	Dev			IE		
Table 14.1.3.1	Demography	Full Analysis Population	Demo		ENROLL/CDD/ HGGD/PBLES/ VS2	DM/DD/DS/ CM/ EX/QS	ADSL	Demo table is done
Table 14.1.3.2	Baseline Characteristics	Full Analysis Population	BasChar		ENROLL/CDD/ HGGD/PBLES/ VS2	DM/DD/DS/ CM/ EX/QS	ADSL	BasChar table is done
Table 14.1.4	Medical History	Full Analysis Population	Mhx			MH	ADMH	MHx table is done
Table 14.1.5	High Grade Glioma Diagnosis	Full Analysis Population	Diagh		ENROLL/CDD/ HGGD/PBLES/ VS2	DM/DD/DS/ CM/ EX/QS	ADSL	Diagh table is done
Table 14.1.6	Prior Cancer Treatments	Full Analysis Population	Canhist			CM/PR	ADCM	
Table 14.1.7	Previous Medications	Full Analysis Population	Meds			CM/PR	ADCM	
Table 14.1.8	Concomitant Medications	Full Analysis Population	Meds			CM/PR	ADCM	
Table 14.2	Best Overall Response	Per Protocol Population	BOR					
Table 14.2.1	Best Overall Response Concordance	Per Protocol Population	BORC					

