Table 14.3.1.13	Treatment-Related Treatment Emergent Adverse Events by Preferred Term in Decreasing Frequency	Full Analysis Population	AEPT			AE	ADAE	AEPT tables are done
Table 14.3.4.1	Listing of Abnormal Laboratory Values		Sig_lab		LAB_NORMLAB/ LBCHEM1/ LBCOAG1/ LBHEMA1/ LBTHYR/LBURIN1 /LBURIN2	LB	ADLB	
Table 14.3.4.2	Listing of Clinically Significant Laboratory Values		Sig_lab			LB	ADLB	
Table 14.3.5.1	Ad-RTS-hIL-12 Injections	Full Analysis Population	Exp1			EX/EC	ADEX	
Table 14.3.5.2	Veledimex Exposure	Full Analysis Population	Exp2			EX/EC	ADEX	
Table 14.3.5.3	Cemiplumab Exposure	Full Analysis Population	Exp3			EX/EC	ADEX	
Table 14.3.6.1	Summary of Serum Chemistry Results	Full Analysis Population	Lab			LB	ADLB	
Table 14.3.6.2	Clinical Significance of Serum Chemistry Results	Full Analysis Population	Lab2			LB	ADLB	
Table 14.3.6.3	Summary of Hematology Results	Full Analysis Population	Lab			LB	ADLB	
Table 14.3.6.4	Clinical Significance of Hematology Results	Full Analysis Population	Lab2			LB	ADLB	
Table 14.3.6.5	Summary of Coagulation Results	Full Analysis Population	Lab			LB	ADLB	
Table 14.3.6.6	Clinical Significance of Coagulation Results	Full Analysis Population	Lab2			LB	ADLB	
Table 14.3.6.7	Summary of Urinalysis Results	Full Analysis Population	Lab			LB	ADLB	
Table 14.3.6.8	Clinical Significance of Urinalysis Results	Full Analysis Population	Lab2			LB	ADLB	
Table 14.3.7	Summary of KPS	Full Analysis Population	KPS			QS	ADQS	
Table 14.3.8	Summary of Vital Signs	Full Analysis Population	Vitals					
Table 14.3.9	Summary of Weight	Full Analysis Population	Weight					
Table 14.3.10	Targeted Neurological Exam	Full Analysis Population	Neuro					
Table 14.3.11	ECG Findings	Full Analysis Population	ECG1			EG	ADEG	
Table 14.3.12	Summary of ECG Results	Full Analysis Population	ECG2			EG	ADEG	
Table 14.3.13	Dose Limiting Toxicities	Per Protocol Population	DLT					
Figure 14.2.3	Kaplan Meier plot of Progression Free Survival by Veledimex Dose							
Figure 14.2.4	Kaplan Meier plot of Overall Survival by Veledimex Dose							
Figure 14.2.5	Kaplan Meier plot of Progression Free Survival by Group							

Figure 14.2.6	Kaplan Meier plot of Overall Survival by Group						
Figure 14.2.7	Forest Plot	Per Protocol Population	FPLT				
Listing 16.2.1	Subject Disposition	Full Analysis Population	L_Disp				

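### SAP 9.2 rules out unit conversion on the premise of a central laboratory, but the SAP's own outputs and the current protocol point to site results

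*Protocol*

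**What the plan says.** SAP 9.2 opens with the premise "Laboratory assessments will be performed by a central laboratory" and draws the rule from it: "All summaries will be based on the units provided by the central laboratory, no conversion will be done". It then plans numeric output: "Summary tables will be presented for clinical laboratory tests with numeric values for subjects in the FAS". The same section plans shift tables by Low, Normal and High, a summary of extreme post-baseline results, and a rule that picks the worst of several values within a visit.

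Three current protocol sections bear on where the results come from:

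- Section 9.1, criterion 8h: "International normalized ratio (INR) and activated partial thromboplastin time (aPTT) or partial thromboplastin time (PTT) within normal institutional limits".
- Section 12.3.1.7: "The coagulation panel includes activated partial thromboplastin time (aPTT) or partial prothrombin time (PTT) and prothrombin time (PT) or INR". SAP 9.2.4 repeats these alternatives.
- The Day 3 visit (section 12.3.2.6, also a footnote to Table 1): "The Day 3 dose should be held until Day 3 labs have been reviewed".

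In the output lists of SAP section 13, Listing 16.2.8.5 is titled "SI Units and Conversion Factors", and Table 14.3.4.1 names as RAW sources "LAB_NORMLAB/ LBCHEM1/ LBCOAG1" and further panel datasets.

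**The concern.** A no-conversion rule does no harm when one laboratory measures everything in one set of units. Applied to results from about 10 centers, it allows values in different units to enter the same mean, minimum or maximum. Such a statistic has no meaning, and a site on a different unit could create or hide an apparent laboratory signal.

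The laboratory tables matter more here than usual. The safety profile is the protocol's primary safety endpoint, and laboratory abnormalities are part of its evaluation. SAP 10.6 removes vital signs, physical and neurological examination and ECG from the abbreviated report, but not the laboratory data.

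**Working it through.** The plan gives no figure to reproduce. The check sets the passages side by side, then adds one illustration.

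**1. What the protocol says about the laboratory.** The visible text names one central facility, the imaging laboratory (sections 13.1 and 13.3). Four features fit site results:

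- The clotting criterion uses institutional limits (9.1, 8h).
- Day 3 results must be seen before that day's dose, and the investigator reviews tests drawn in the 24 hours before surgery (Table 1 footnotes).
- Section 12.1 lets routine tests done before consent count as screening if they fall in the window.
- The clotting panel is written as alternatives (12.3.1.7), whereas the Table 1 footnote and the screening list name only aPTT and INR.

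The third feature can reach the analysis. The coagulation panel is scheduled at screening and Day 0 but not at Day -7. SAP 4.6 takes baseline as the last value before the first dose of any study drug, which is cemiplimab at Day -7. The scheduled coagulation baseline is therefore the screening value, and that may be a routine site test.

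**2. What the SAP says about the data path.** SAP 4.4 extracts RAW datasets from the EDC database and says the seven external vendors supply data that are not on the eCRF. The second output list maps the laboratory panels to RAW datasets, including LAB_NORMLAB, whose name suggests laboratory normal ranges. These feed LB and ADLB, the same datasets used for the summary tables 14.3.6.1 to 14.3.6.8. By the SAP's own description, this is the eCRF path and not the vendor path.

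**3. Whether the SAP is consistent on conversion.** A listing of SI units and conversion factors has little purpose if nothing is converted. SAP 6.1 and 9.3 also convert height, weight and temperature, so the SAP expects mixed units for other site-recorded values. Only laboratory values are barred.

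**4. Which outputs depend on units.**

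| Output | Exposed to mixed units? |
|---|---|
| Numeric summaries, extreme post-baseline values | Yes |
| Worst value within a visit | Yes, if values from two sources meet at one visit |
| Low/Normal/High shifts | Less, if each value is judged by its own laboratory's range |
| Overall survival | No |
| Toxicity boundary | No; it counts subjects meeting the stopping criteria, not pooled laboratory values |

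**5. Illustration (assumed; the documents give no shares).** Let a share f of records for one test be in a unit whose numbers are ten times as large, such as g/L against g/dL, with the same true mean. Then

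pooled mean / true mean = (1 − f) + 10f = 1 + 9f.

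| f | Multiplier |
|---|---|
| 0% | 1.00 |
| 5% | 1.45 |
| 10% | 1.90 |
| 25% | 3.25 |
| 50% | 5.50 |

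With 10 centers contributing equally to the 40 treated subjects (an assumption), one center is 4/40 = 10%.

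**The case against.** The SAP states positively that there is a central laboratory, and the protocol never denies it. Parts of the protocol are redacted and the SAP's vendor table is not visible, so a central vendor cannot be excluded. Day 3 review, pre-surgery review and institutional limits concern eligibility and management; they are compatible with local results for care and central results for analysis. The institutional limits attach only to INR and aPTT/PTT. Dataset names do not prove several laboratories, and an EDC database can hold central values. References to OSHA, FDA Form 1572 and HIPAA suggest US sites, which makes a wide mix of units less likely. Abnormal results are also captured as adverse events and listed by subject, so a gross unit error would probably be seen.

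Most of this stands as a limit on certainty and size. It does not remove the SAP's internal conflict: a rule against conversion beside a listing of conversion factors, and a central-laboratory premise beside an EDC data path. The listing itself needs care. It is visible only in the first of the two output lists, and the available text of the second stops at Listing 16.2.6.8, before the laboratory listings. It may also mean that standardisation was intended, in which case the sentence in SAP 9.2 is what is wrong.

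A reader might infer that PT in seconds and INR would be averaged together. The documents do not say that they share a parameter; they only fail to say that they are separate. Nor do they support the reading that the protocol rules out a central laboratory, or that the pooled values will in fact be wrong.

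**Conclusion.** The point holds as an inconsistency to be resolved before the laboratory tables are produced. SAP 9.2 fixes a rule on a premise that the SAP's output lists and data-flow section contradict and that current protocol sections make doubtful. If the analysed values are site results, the rule could pool mixed units in numeric summaries and extreme values.

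That sites supplied the values is an inference from timing, ranges and data path, not a statement in the documents. The effect may be nil if all sites report in the same units; the multipliers above show only how fast it grows if they do not. It is confined to descriptive laboratory outputs. The wording gap on PT, INR, aPTT and PTT remains whichever laboratory was used.

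**What to change.** In SAP 9.2:

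1. State the actual source of the analysed laboratory values.
2. Delete the clause that bars conversion. Standardise each test to one unit before any numeric summary or worst-value selection, using the factors in Listing 16.2.8.5, and confirm that this listing is kept in the final output list.
3. Classify Low, Normal and High against the reporting laboratory's own range.
4. Define PT, INR, aPTT and PTT as four separate parameters in SAP 9.2.4.
5. If a central laboratory did supply the analysed values, say so and exclude local values from the summary tables.

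The cost is a few sentences of SAP text and routine programming. The conversion listing and what appears to be a normal-range dataset are already named in the output lists, and no new data are needed if units and ranges were recorded with the results.
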